#### **END OF INTERVIEWER-ADMINISTERED QUESTIONNAIRE**

Thank you for taking the time to complete the interview. This information is vitally important to our study and we greatly appreciate your contributions.

#### **INTERVIEWER'S REMARKS**

1.	Participant ID
2.	Interviewer (Initials)
3.	Participant's date of birth MonthDayYear (Current Age:)
4.	Date of Interview MonthDayYear
5.	Interview Start Time:(Hour: Minutes [24-hour time])
6.	Interview End Time : (Hour: Minutes [24-hour time])
7.	The interview included: (Check all boxes that apply.)  1 The participant only 2 A spouse or partner 3 Another family member 4 Another person (please specify)
8.	The participant's cooperation was: (Check one box only.)  Excellent  Very Good  Good  Fair  Poor
9.	The quality of the interview is: (Check one box only.)  Excellent  Generally reliable  Questionable  Unreliable

#### APPENDIX F

Participant ID:	
Date:	

# Preventive Human Papillomavirus (HPV) Vaccine Trial in Kidney Transplant Recipients

## **Follow-Up Questionnaire**

We appreciate the time you are taking to complete this interview. We will be asking you questions that focus on any changes that may have occurred since your last research visit for this study on\_ (date of last study visit). Please try to answer each question as completely as you can, even if you are unsure about the answer. If you feel uncomfortable answering any question, you can choose not to answer it. All answers will be kept confidential.

#### **PHYSICAL HEALTH AND FRAILTY**

	The first questions ask about your physical health. << Components of the FRAIL AAH Questionnaire >>					
1.	How much do you currently weigh with your clothes on but without shoes?Pounds					
2.	How much of the time during the past 4 weeks did you feel tired? Please select one answer only.  All of the time  Most of the time  Some of the time  A little of the time  None of the time					
3.	By yourself and not using aids, do you have any difficulty walking up 10 steps without resting ?  ¹ Yes ° No					
4.	By yourself and not using aids, do you have any difficulty walking several hundred yards?  Yes One No					
	SF-12® HEALTH SURVEY					
	This set of questions asks for your views about your health since your last research study visit on(date of last study visit). If you are unsure about how to answer a question, please give the best answer youcan.					
1.	In general, would you say your current health is (please select one answer only):  1 Excellent  2 Very Good  3 Good  4 Fair  5 Poor					
2.	The following questions are about activities you might do during a typical day. Does your health now limit you in these activities? If so, how much?					
	Yes, limited Yes, limited No, not a little limited at all					
	a. Moderate activities, such as moving a table, pushing a vacuum cleaner, bowling, or playing golf					
	b. Climbing several flights of stairs					
3.	During the past 4 weeks, have you had any of the following problems with your work or other regular daily activities as a result of your physical health?					
	a. Accomplished less than you would like  Yes  1  2					
	b. Were limited in the kind of work or other activities 1 2					
4.	During the past 4 weeks, have you had any of the following problems with your work or other regular daily activities as a result of any emotional problems (such as feeling depressed or anxious)?  Yes No  a. Accomplished less than you would like					
	b. Did work or activities less carefully than usual					
5.	During the past 4 weeks , how much did pain interfere with your normal work (including both work outside the home and housework)? Please select one answer only.  Not at all  A little bit  Moderately  Quite a bit  Extremely					
6.	These questions are about how you feel and how things have been with you during the past 4 weeks.  For each question, please give the one answer that comes closest to the way you have been feeling.  How much of the time during the past All of the time the time of the time					
7.	During the past 4 weeks , how much of the time has your physical health or emotional problems interfered with your social activities (like visiting friends, relatives, etc.)? Please select one answer only.  1 All of the time 2 Most of the time 3 Some of the time 4 A little of the time 5 None of the time					

	SKIN TYPE, SUN EXPOSURE, A	ND SUN PR			antiguesco perio	NWU2015-06-02 ecember 23, 2020
7	he next questions ask about your skin, sun exposure, and	NUMBER OF STREET		3100000	search	study visit.
1.	Since your last research study visit on, have you ha	ad a full bo	dy skin e	xam by a de		
2.		ovider told Piagnosis da Mon/Day/\	ate	1	reatme	ition)? ent Received enter None)
	a. Atypical moles	 				
	b. Benign skin lesions	—//_				
	c. Skin cancer (If YES, ask question # 3)	_/_/_			9 7 7 7 7 7 7 7 7 7 7 7 7 7 7 7 7 7 7 7	
	If Question # 2c is Yes, ask: What type of skin cancer?  Basal Delta Squamous Delta Melanoma Delta Heror the following questions, think about what you do what you	emangiom en you are		Don't know		nny day.
	Select one response for each question.	Never	Rarely	Sometime	s Oft	en Always
	a. How often do you wear SUNSCREEN?	0	1	2	3	4
	b. How often do you wear a SHIRT WITH SLEEVES that covers your shoulders?	0	1	2	3	4
	c. How often do you wear a HAT?	0	1	2	3	4
	d. How often do you stay in the SHADE or UNDER AN UMBRELLA?	0	1	2	3	4
	e. How often do you wear SUNGLASSES?	0	1	2	3	4
5.	In the past month, how many times did you have skin irr your skin was irritated for more than 12 hours? Select on		100	ytime that e	ven a s	mall part of
	0 1 2 3 4	5 or more	9			
	0 1 2 3 4	5				
6.	Please indicate whether you agree or disagree with each	of the follo	owing sta	tements.		
	, 3 3				gree	Disagree
	a. People with a kidney transplant take medicine that m sensitive to the sun.	ay make th	neir skin		1	2
	b. Only people with a kidney transplant that have sun sensitive skin, who freckle and sunburn easily, have to worry about getting a skin cancer.					2
	c. Applying sunscreen after being out in the sun is enough protection.					2
	d. When the sun is high in the sky, seek shade to avoid the strong rays of the sun.					2
	e. Clothing does not protect the skin from the sun.					2
	f. Sunglasses protect the delicate skin around the eyes.				1	
	i. Sunglasses protect the delicate skin around the eyes.					
	g. It takes about a teaspoon of sunscreen to cover the sl	kin of the v	vhole boo	dy.	1	2
		kin of the v	vhole boo	dy.	1	2

Select one answer for each statement.	Strongly Disagree	Disagree	Undecide	d Agree	Strongl Agree
a. I am at risk of developing skin cancer.	1	2	3	4	5
b. Skin cancer does not kill people.	1	2	3	4	5

 
Regular use of sun protection helps to prevent skin cancer.
 
	1	2	3	4	5

 
d. The transplant doctors and nurses seem to feel that I should use sun protection.
 
	1	2	3	4	5
e. It is important to my partner that I use sun protection.	1	2	3	4	5
f. I look better with a tan.	1	2	3	4	5
g. I look healthier with a tan.	1	2	3	4	5
MEDICAL HI					
The following questions ask about your medical	history sin	ce your las	st research s	study visit.	
b. Was your most recent Pap smear abnormal?	(Mor	procedure nth/Day/Ye ∘	ear)		
b. Was your most recent Pap smear?  b. Was your most recent Pap smear abnormal?  1 males only:  Since your last research study visit on, have you	(Mor	o No	ving medica	nen did you	ı have
b. Was your most recent Pap smear?  b. Was your most recent Pap smear abnormal?  1 males only:	(Mor	oth/Day/Ye ○ No	ving medica		u have edure]?
b. Was your most recent Pap smear?  b. Was your most recent Pap smear abnormal?  inales only:  Since your last research study visit on, have you	Yes (Mor	oth/Day/Ye ○ No	ving medica Wi	nen did you dical proce	u have edure]?
b. Was your most recent Pap smear? b. Was your most recent Pap smear abnormal?  inales only:  Since your last research study visit on, have you  If Yes, ask date of medical procedure.	Yes Yes	o No	ving medica Will Don't [meknow]	nen did you dical proce	u have edure]?
b. Was your most recent Pap smear?  b. Was your most recent Pap smear abnormal?  inales only:  Since your last research study visit on, have you  If Yes, ask date of medical procedure.  a. Repeat/follow-up Pap smear	(Mor	the follow	ving medica Will Don't [meknow]	nen did you dical proce	u have edure]?
b. Was your most recent Pap smear?  b. Was your most recent Pap smear abnormal?  imales only:  Since your last research study visit on, have you  If Yes, ask date of medical procedure.  a. Repeat/follow-up Pap smear  b. Colposcopy	Yes	the follow	ving medica WI Don't [meknow]	nen did you dical proce	u have edure]?
b. Was your most recent Pap smear? b. Was your most recent Pap smear abnormal?  inales only:  Since your last research study visit on, have you  If Yes, ask date of medical procedure.  a. Repeat/follow-up Pap smear  b. Colposcopy  c. Freezing or cryotherapy of the cervix	Yes	the follow  No  No  Output	ving medica Will Don't [meknow]  y	nen did you dical proce	u have edure]?
b. Was your most recent Pap smear?  b. Was your most recent Pap smear abnormal?  males only:  Since your last research study visit on, have you  If Yes, ask date of medical procedure.  a. Repeat/follow-up Pap smear  b. Colposcopy  c. Freezing or cryotherapy of the cervix  d. Burning or laser therapy of the cervix	had any of	the follow  No  No  Output	ving medica WI Don't [meknow]  9 9 9	nen did you dical proce	u have edure]?
b. Was your most recent Pap smear?  b. Was your most recent Pap smear abnormal?  imales only:  Since your last research study visit on, have you  If Yes, ask date of medical procedure.  a. Repeat/follow-up Pap smear b. Colposcopy c. Freezing or cryotherapy of the cervix d. Burning or laser therapy of the cervix e. Biopsy of the cervix (If YES, also ask question # 3)	Yes  1 1 1 1 1	No	ving medica Will Don't [me know 9	nen did you dical proce	u have edure]?
b. Was your most recent Pap smear?  b. Was your most recent Pap smear abnormal?  males only:  Since your last research study visit on, have you  If Yes, ask date of medical procedure.  a. Repeat/follow-up Pap smear  b. Colposcopy  c. Freezing or cryotherapy of the cervix  d. Burning or laser therapy of the cervix  e. Biopsy of the cervix (If YES, also ask question # 3)  f. Surgery of the cervix (including conization or LEEP)  g. D & C (Dilation and Curettage)  h. Hysterectomy (removal of your uterus)	Yes  i i i i i i i i i i i i i i i i i i i	the follow  No  No  Output  No  Output  No  Output  Ou	ving medica Will Don't [meknow]  9	nen did you dical proce	u have edure]?
b. Was your most recent Pap smear?  b. Was your most recent Pap smear abnormal?  males only:  Since your last research study visit on, have you  If Yes, ask date of medical procedure.  a. Repeat/follow-up Pap smear  b. Colposcopy  c. Freezing or cryotherapy of the cervix  d. Burning or laser therapy of the cervix  e. Biopsy of the cervix (If YES, also ask question # 3)  f. Surgery of the cervix (including conization or LEEP)  g. D & C (Dilation and Curettage)	Yes  i i i i i i i i i i i i i i i i i i i	No No O O O O O O O O O O O O O O O O O	ving medica Will Don't [me know 9	nen did you dical proce	u have edure]?
b. Was your most recent Pap smear?  b. Was your most recent Pap smear abnormal?  males only:  Since your last research study visit on, have you  If Yes, ask date of medical procedure.  a. Repeat/follow-up Pap smear  b. Colposcopy  c. Freezing or cryotherapy of the cervix  d. Burning or laser therapy of the cervix  e. Biopsy of the cervix (If YES, also ask question # 3)  f. Surgery of the cervix (including conization or LEEP)  g. D & C (Dilation and Curettage)  h. Hysterectomy (removal of your uterus)	Yes  i i i i i i i i i i i i i i i i i i i	No O O O O O O O O O O O O O O O O O O O	ving medica Will Don't [medica know]  9	nen did you dical proce	u have edure]?

#### **ALCOHOL AND TOBACCO USE**

	The next questions ask about your use of alcohol and tobacco since your last research study visit.					
1.	How often do you have a drink containing alcohol? If NEVER skip to question # 4 (cigarette smoking) O Never D Monthly or less D 2-4 times a month D 2-3 times a week  4 4 or more times a week					
2.	How many standard drinks containing alcohol do you have on a typical day? A standard drink is a 12-ounce bottle or can of beer, a 4-ounce glass of wine, a shot of liquor, or a mixed drinkdrinks					
3.	How often do you have six or more drinks on one occasion?  Output  Description:  Weekly A Daily or almost daily					
4.	Since your last research study visit on (date of last study visit), have you smoked cigarettes?  1 Yes  1 No $\rightarrow$ If NO skip to next section – SEXUAL HISTORY					
5.	When did you last smoke a cigarette? (Month/Day/Year)					
6.	How many cigarettes do you usually smoke each day ? cigarettes per day					
	SEXUAL ACTIVITY					
	he last questions ask about your sexual activity since your last research study visit on(date of last visit). We ask you these questions because human papillomavirus (HPV) is spread primarily through sexual contact.  You can skip any questions you feel uncomfortable answering.					
6	Have you been sexually active since your last research study visit on?  □¹ ☐ Yes □ ☐ No → If NO the interview is completed  >a. With how many partners have you been sexually active since your last study visit? partners					
Fer	males only:					
	Since your last research study visit, have you had sexual (vaginal) intercourse with a male partner?  The second of the sexual intercourse since your last study visit? Interviewer: probe for frequency.  The second of the sexual intercourse since your last study visit? Interviewer: probe for frequency.  The second of the sexual intercourse since your last study visit? Interviewer: probe for frequency.  The second of the sexual intercourse since your last study visit? Interviewer: probe for frequency.  The second of the sexual intercourse since your last study visit? Interviewer: probe for frequency.  The second of the sexual intercourse since your last study visit? Interviewer: probe for frequency.  The second of the sexual intercourse since your last study visit? Interviewer: probe for frequency.  The second of the sexual intercourse since your last study visit? Interviewer: probe for frequency.  The second of the sexual intercourse since your last study visit? Interviewer: probe for frequency.  The second of the sexual intercourse since your last study visit? Interviewer: probe for frequency.  The second of the sexual intercourse since your last study visit? Interviewer: probe for frequency.  The second of the sexual intercourse since your last study visit? Interviewer: probe for frequency.  The second of the sexual intercourse since your last study visit? Interviewer: probe for frequency.  The second of the sexual intercourse since your last study visit? Interviewer: probe for frequency.  The second of the sexual intercourse since your last study visit? Interviewer: probe for frequency.  The second of the sexual intercourse since your last study visit? Interviewer: probe for frequency.  The second of the sexual intercourse since your last study visit? Interviewer: probe for frequency.  The second of the sexual intercourse since your last study visit? Interviewer: probe for frequency.  The second of the sexual intercourse since your last study visit? Interviewer: probe for frequency.  The second of the sexual					
Fer	males only:					
6	3. Since your last study visit, have you had oral sex with a male partner?  1 Yes					
Ma	ales only:					
2.	Since your last research study visit, have you had sexual intercourse?  Yes $ ^{\circ} \square \text{ No} \rightarrow \text{If NO skip to question } \# 3 $ a. How often have you had sexual intercourse since your last study visit? Interviewer: probe for frequency.  1 \[ 1-2 \times \text{since last visit} \]  2 \[ 3-5 \times \text{since last visit} \]  4 \[ 2-3 \times \text{per month} \]  5 \[ 1 \text{ or more times per week} \]					

NWU2015-06-02 Protocol Version 3.10, December 23, 2020

Males only:

3. Since your last study visit, have you $\square$ Yes $\square$ No $\rightarrow$ If NO the in	terview is completed	
a. How often have you had oral se	ex since your last study visit? Intervie  3-5 times since last visit  1 or more times per week	ewer: probe for frequency.  3 Once per month

### **END OF INTERVIEWER-ADMINISTERED QUESTIONNAIRE**

Thank you for taking the time to complete the interview. This information is vitally important to our study and we greatly appreciate your contributions.

#### **INTERVIEWER'S REMARKS**

1.	Participant ID
2.	Study Visit Number  Second  Third  Fourth
3.	Date of This Study Visit MonthDayYear
4.	Date of Last Study Visit MonthDayYear
5.	Interviewer(Initials)
6.	Interview Start Time :(Hour: Minutes [24-hour time])
7.	Interview End Time :(Hour: Minutes [24-hour time])
8.	The interview included: (Check all boxes that apply.)  1 The participant only 2 A spouse or partner 3 Another family member 4 Another person (please specify)
9.	The participant's cooperation was: (Check one box only.)  Excellent  Very Good  Good  Fair  Poor
10.	The quality of the interview is: (Check one box only.)  Excellent  Generally reliable  Questionable  Unreliable

#### APPENDIX G

#### **COVID-19 Contingency Plan**

**Background**: In response to the public health emergency due to the COVID-19 pandemic, several adaptations have been included to ensure that the protocol will be able to meet its primary endpoint. This Appendix lists the specific modifications to the protocol that may be permitted to be undertaken in the context of the COVID-19 Contingency plans.

1. Remote Specimen Collection: Considering the closure of several study clinics to non-emergency study visits due to the COVID-19 crisis and concerns about SARS-COV2 transmission, an alternative plan for remote specimen collection will be offered to eligible and affected participants. This includes an at-home self-collection of a cervical/vaginal specimen that is described in the protocol and would also be self-collected in clinic. In addition, we include an at-home finger stick capillary blood collection of a dried blood spot via a novel sample collection device (Neoteryx Mitra cartridge). This device is based on volumetric absorptive microsampling (VAMS) technique that has been previously evaluated in measuring vaccine antibody responses and other biomarkers (See references below). Incorporating this device will allow the possibility of measurement of HPV antibody responses closer to the original/protocol-specified visit time points when COVID-19-related concerns preclude the possibility of in-person clinic visits. The procedures for remote specimen collection includes an addendum consent (APPENDIX H) for an at-home finger-stick capillary blood collection (dried blood spot) via a special collection device and return shipment of the specimen, along with phone calls to review medical and surgical history, medications, symptom assessment, determination of ECOG performance status and administration of study questionnaire.

#### **Applicable visits:**

- 6-months post-transplant visit
- 12-months post-transplant visit
- 13-months post-transplant visit (to be conducted only if, and 1-month after, any original scheduled or rescheduled in-person 12-month post-transplant visit is conducted).

#### **Procedures:**

- 1. Study staff will identify appropriate participants affected by the cancellation/deferral of regularly scheduled study visits.
- 2. Eligible participants will be contacted by phone and procedures will be explained by the study investigators and staff.
- 3. Participants will be administered the remote consent as per COVID-19 remote consent procedures approved by the CIRB. (see 'Appendix H')
- 4. Staff will interview the participants for review of medical and surgical history, medications, symptom assessment, determination of ECOG performance status, and follow-up questionnaire for the 6-months and 12-months visits.
- 5. Participants will be sent an Evalyn cervical/vaginal specimen collection kit, and a Neoteryx Mitra sampling cartridge. All collection kits will have standardized instructions and study specific information sheets (see 'Finger Stick Participant Information material' and 'Vaginal Self-Collection Instructions'). All devices and return collection kits will have barcoded labels that confidentially link back to the participant record without any identifying information (participant name, other contact details, etc.).
- 6. Participants will self-collect a personal cervical/vaginal specimen and a finger stick blood specimen and will return to the Cedars Sinai biorepository using pre-labeled, pre-paid packages that will be picked up by a courier at the participant's home or pre-arranged location.

- 2. **Expansion of window for 12-months post-transplant visit for specimen collection for primary endpoint:** The visit for specimen collection for the primary endpoint (12-months post-transplantation time point) is regularly scheduled at 12-months +/- 2 weeks after the transplant surgery. The +/- 2 weeks window will now be extended to *up to +/- 6 months* to permit maximum operational flexibility due to the scheduling challenges due to COVID-19, and may be rescheduled to a convenient date and time once it is considered safe to resume study activities.
- 3. **6-months post-transplant study visits:** The rescheduled 12-month post-transplant visit (for the primary endpoint) now includes a very broad/expanded window (+/- 6 months) that may overlap with the original 6-month post-transplant visit timeframe. The 6-month post-transplant visit will therefore be considered an optional one due to the COVID-19-related scheduling challenges.
- 4. **13-months post-transplant study visits**: This visit will also be considered an optional one and can now be rescheduled to occur one month (+/- 2 weeks) after the rescheduled 12-month post-transplant visit, only for participants who have received the booster injection.
- 5. **Visit procedures:** All procedures in Section 7 "CLINICAL EVALUATIONS AND PROCEDURES" corresponding to the rescheduled visits will be conducted as outlined. In addition, cervical/vaginal, and blood specimens may occur for eligible and consenting participants for the 6-months, 12-months, and 13-months (finger stick only) post-transplant visits.
- 6. **Specimen Management:** The finger-prick collection method will yield dried blood spot collection that will be stored in the biorepository at Cedars Sinai Medical Center for future analysis for the HPV serological analysis for the primary and secondary endpoints. The cervical/vaginal specimens will be used per protocol for analysis of secondary aims.
- 7. **Participant reimbursement**: For participants seen under the COVID-19 Contingency Plan compensation will be per protocol.

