# Vaccine Doses and Timing in relation to Transplant Surgery and Immunosuppression.

Current (2018) CDC recommendations suggest that Gardasil® 9 be given in a 3-dose schedule at 0, 2, and 6 months for immunocompromised individuals (such as transplant recipients) between the ages of 16 and 45 years. (There are no recommendations for vaccination for individuals over 45 years of age, and such use is considered off-label.) Furthermore, there are no recommendations on the optimal number and timing of doses in relation to the transplant surgery. This trial will seek to enroll both living-donor and deceased-donor transplant recipients, and the number and timing of vaccine doses will be dependent on two factors:

- i. The time remaining between enrollment date and transplant surgery.
- ii. Need for avoiding administering any vaccine doses for at least 12 months in the post-transplant period when the strongest regimens of immunosuppressive medications to prevent transplant rejection are being administered.

Due to these caveats, participants may receive one, two, or three doses of vaccines prior to transplant. If all three doses are not administered before transplant then the rest of the doses in the three dose vaccine

series will be administered at or after 12-months after transplant. An abbreviated schedule of vaccination (permitted by current vaccine label/CDC recommendations) may also be utilized to allow administration of as many vaccine doses prior to transplantation as possible. If participants do not undergo transplant surgery within 12 months of study enrollment and have not received the recommended three dose series in the intervening 12 months, the remaining doses will be offered via Additional Study Visit(s) at 12 months and, if necessary, at 15 months after the first vaccine dose.

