# 12 Month Post-Transplant Visit

This study visit will occur 12 months ( $\pm$  2 weeks) after the participant's kidney transplant procedure. The following procedures will be performed during this visit:

- 1) Review of medical and surgical history, medications, and laboratory test results
- 2) Symptom assessment and ECOG performance status
- 3) Physical exam including vital signs and measurement of weight
- 4) Pregnancy test (urine or blood) for women who meet both of the following criteria:
  - a. Received only one or two vaccines earlier in the study, AND
  - b. Are able to become pregnant (women who have had both ovaries removed or a tubal ligation will not be required to have a pregnancy test)

Women who are pregnant will not receive the Gardasil® 9 HPV vaccine.

- 5) Participants who have received two vaccine doses prior to transplant will receive the third dose of the vaccine. Participants who have received only one dose of the vaccine prior to transplant will receive the second dose of the vaccine at this visit.
- 6) Blood draw A 28 mL blood specimen will be collected from each participant.
- 7) Self-collection of cervical/vaginal and oral samples for HPV DNA detection.
- 8) Self-collection of urine for HPV DNA detection from participants who consent to collection of optional urine samples.
- 9) Self-collection of male genital samples for future HPV DNA testing from participants who consent to collection of these optional samples for biobanking for future studies
- 10) Collection of eyebrow hairs (collected by research staff) for future viral DNA testing from participants who consent to collection of optional samples for biobanking for future studies
- 11) Interviewer-administered follow-up questionnaire to obtain information about changes in exposures and behaviors between study visits (Appendix F)
- 12) Review of inclusion/exclusion criteria and study requirements

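### Appendix G moves the 12-month visit, and read literally its vaccine dose, to as early as 6 months post-transplant, against the dose timing in Sections 2.3, 3 and 5.1

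*Combined protocol and SAP*

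**What the plan says.** **Dose timing.** Section 2.3 (Vaccine Doses and Timing) names two factors that govern the number and timing of doses. One is the "Need for avoiding administering any vaccine doses for at least 12 months in the post-transplant period", because immunosuppression is heaviest then. Where three doses are not completed before transplant, the rest of the "series will be administered at or after 12-months after transplant". Section 3 repeats this for the second and third doses. Table 2 in Section 5.1 sets the first post-transplant dose at 12 months ±2 weeks.

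**The 12-month visit.** Section 7.4 puts the visit at 12 months ±2 weeks and builds the dose into it: "Participants who have received two vaccine doses prior to transplant will receive the third dose of the vaccine", and "Participants who have received only one dose of the vaccine prior to transplant will receive the second dose of the vaccine at this visit". A 28 mL blood sample is drawn at the same visit.

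**The contingency plan.** Appendix G item 2 is headed "Expansion of window for 12-months post-transplant visit for specimen collection for primary endpoint" and extends the window to as much as 6 months either side. Item 3 says that the rescheduled visit "now includes a very broad/expanded window (+/- 6 months) that may overlap with the original 6-month post-transplant visit timeframe" and makes the 6-month visit optional. Item 4 places the 13-month visit one month (±2 weeks) after the rescheduled 12-month visit, for boosted participants only. Item 5 says that all Section 7 procedures "corresponding to the rescheduled visits will be conducted as outlined". It makes no exception for the vaccine.

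**The concern.** A site has two sets of instructions. One says that no dose falls in the first 12 months after transplant. The other says to hold the 12-month visit any time from month 6 and to carry out its listed procedures, one of which is the dose. Appendix G neither repeats the 12-month minimum nor says whether the dose stays where Table 2 puts it when the visit moves.

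Two things are at stake. Sites could act differently on a question of dose timing that the protocol itself treats as important. And an early booster changes what later blood samples mean: they reflect pre-transplant doses plus a booster, not pre-transplant doses alone. The exploratory 13-month rise would then pool boosters given at very different intervals after transplant.

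**Working it through.** **Inputs.** Regular 12-month visit and post-transplant dose: 12 months ±2 weeks (Section 7.4, Table 2). Contingency window: ±6 months (Appendix G, items 2 and 3). 6-month visit: 6 months ±2 weeks (Section 7.4). Minimum for a post-transplant dose: 12 months (Sections 2.3 and 3). 13-month visit under contingency: 1 month ±2 weeks after the rescheduled visit (Appendix G, item 4). Evaluable participants: 24 to 28 (Section 13.4). One month is taken as 365.25/12 = 30.44 days.

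**1. The plan's own statement that the windows overlap.**
- 6-month visit: 182.6 ± 14 = 168.6 to 196.6 days.
- Expanded 12-month visit: 365.25 ± 182.6 = 182.6 to 547.9 days, that is 12 − 6 = 6 to 12 + 6 = 18 months.
- The lower end, 182.6 days, lies inside 168.6 to 196.6. The overlap is confirmed.

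**2. Distance from the dose timing.**
- Against Sections 2.3 and 3: 12 − 6 = 6 months early at the window edge.
- Against Table 2: its earliest day is 365.25 − 14 = 351.2, and 351.2 − 182.6 = 168.6 days, or about 5.5 months, early.

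**3. Does the dose move with the visit?**

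| Text | Points to |
|---|---|
| Item 2 heading | Specimen collection only |
| Item 3 | The visit itself may fall near month 6 |
| Item 5 with Section 7.4 | All visit procedures, so the dose as well |
| Item 4 | A booster is expected by the rescheduled visit; its timing is not stated |
| Table 2 (not mentioned in Appendix G) | Dose stays at 12 months ±2 weeks |

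No sentence separates the dose from the visit. Both readings can be argued, and they give different dose dates.

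**4. Samples after an early dose.** Suppose the visit and dose fall at month 6. Blood is drawn at that visit. If it is taken before the injection it is a pre-booster sample, but at month 6; Section 7.4 lists the vaccine and then the blood draw without stating an order. Every later sample is post-booster. Two weeks is 14/30.44 = 0.46 months, so the 13-month sample could fall as early as 6 + 1 − 0.46 = 6.54 months and, for a late visit, as late as 18 + 1 + 0.46 = 19.46 months post-transplant.

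**5. Who could receive a dose early through Appendix G?**

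| Participant | Early dose possible? |
|---|---|
| Three pre-transplant doses | No; no dose at this visit |
| One or two doses, remote collection | No; kits and phone calls only |
| One or two doses, visit deferred past 12 months | No |
| One or two doses, seen in person ahead of the regular window | Yes, on the literal reading |

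The documents do not say how many people fall in the last row. One such person would be 1/28 = 3.6% to 1/24 = 4.2% of the evaluable set. That is a share of participants, not an estimate of bias.

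**6. Table 3 is unaffected.** Its limits reproduce as the Beta quantile (0.95; x + 1, n − x) with x = nP, all ten cells within 0.0001; for example n = 28, P = 0.90 gives 0.9739, as printed.

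**The case against.** The best defence is that only the specimen moves. Appendix G presents itself as the list of specific protocol changes, and a change of dose timing is not on it. Item 2 is headed and worded around specimen collection. Table 2 is not amended, and item 5 carries over Section 7, not Section 5. The setting also points to delay: clinics were closed, visits were cancelled or deferred, and rescheduling was to wait until study activity could safely restart. No passage describes giving vaccine early.

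Much of this stands as a statement of likely intent, but it does not remove the conflict. The window is written on both sides of 12 months, and item 3 relies on the early side to make the 6-month visit optional. Section 7.4, which item 5 imports whole, contains the dose.

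A reader might also infer three stronger points that the documents do not support:
- **That every one- or two-dose participant under the contingency plan is exposed.** Remote participants receive no dose, and visits deferred past 12 months meet the minimum.
- **That the early booster is what destroys the 12-month primary measurement.** Blood is drawn at the dosing visit, and no second 12-month draw is planned. If the visit is held at month 6, the true 12-month value is missing with or without a booster. That loss comes mainly from the specimen window.
- **That the ordinary ±2-week window breaks the same rule.** It is routine visit tolerance, stated consistently across the sections.

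**Conclusion.** The conflict is real and lies in the current text. On the literal reading, Appendix G permits a vaccine dose up to 6 months before the timing in Sections 2.3 and 3, and outside Table 2. On the specimen-only reading it does not, and the text does not choose between them.

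The exposed group is narrow: one- or two-dose participants seen early and in person. Its size is unknown and may be zero, so no effect on the seroconversion estimate can be calculated. It would be wrong to take the early half of the 6-to-18-month window as the share of participants dosed early; window width is not a probability.

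In anyone dosed early, samples after that visit are post-booster, and the 13-month rise mixes boosters given at different times from transplant. The latter analysis is exploratory and descriptive, and its visit is optional under Appendix G. The conclusion assumes that item 5 means what it says and that the 12-month minimum was not meant to lapse under the contingency plan.

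**What to change.** 1. Reconcile Section 2.3, Section 3, Table 2 in Section 5.1, the 12-month visit in Section 7.4, and Appendix G items 2 to 5. Appendix G should state whether the early side of the expanded window applies to the vaccine dose or to specimen collection only, and the other sections should agree with it. The choice of timing belongs to the sponsor; this review proposes none.
2. For doses already given, derive months from transplant to booster. Describe the 13-month rise separately for boosters given before 12 months and from 12 months onward.

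The cost is a short amendment and one extra split of an exploratory table. The split needs the transplant and vaccination dates, which are assumed to be on file because visits are scheduled from one and dispensing dates are recorded under Section 6.5. The downside is small cells: the table draws on at most 24 to 28 people, less those who had three doses before transplant, and the early group may be empty. If it is empty, saying so in one line settles the point for the analysis.
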